### 5.2.1.4 Dose Limiting Toxicity

For the dose escalation part of this study (Part A), a DLT is defined as any of the following toxicities occurring during the first cycle of treatment (21 days) for each dose level. See Section 5.9 for rules on replacement of subjects in the DLT period.

The occurrence of any of the following toxicities during Cycle 1, **if assessed by the investigator to be possibly, probably or definitely related to MK-8628**, will be considered a DLT:

Hematologic toxicity

- Grade 4 hematologic toxicity lasting  $\geq 7$  days, except thrombocytopenia
  - Grade 4 thrombocytopenia of any duration
  - Grade 3 thrombocytopenia is a DLT if associated with bleeding
- Febrile neutropenia Grade 3 or Grade 4

Non-hematologic toxicity

- Grade 4 non-hematologic toxicity (not laboratory)
- Grade 3 non-hematologic toxicity (not laboratory) lasting  $> 3$  days despite optimal supportive care. Grade 3 nausea, vomiting or diarrhea will be considered a DLT if lasting more than 3 days despite optimal supportive care.
- Any Grade 3 or 4 non-hematologic laboratory abnormality, if:
  - medical intervention is required, or
  - the abnormality leads to hospitalization, or
  - the abnormality persists for  $> 1$  week
- Any of the following liver test abnormalities are observed (see also Section 12.7):
  - ALT or AST  $> 8X$  ULN
  - ALT or AST  $> 5X$  ULN for more than 2 weeks
  - ALT or AST  $> 3X$  ULN **AND** (total bilirubin  $> 2X$  ULN **OR** INR  $> 1.5$ )
  - ALT or AST  $> 3X$  ULN with the appearance of fatigue, nausea, vomiting, right upper quadrant pain or tenderness, fever, rash and/or eosinophilia ( $> 5\%$ ), unless the investigator assesses the rash or fatigue to be related to MK-8628 and not related to liver impairment, with Sponsor's agreement

Other

- Any drug-related AE which caused the subject to discontinue treatment during Cycle 1
- Any study drug-related toxicity resulting in a subject missing  $\geq 20\%$  of planned doses during Cycle 1.
- Any treatment-related toxicity which causes a greater than 2 week delay in initiation of Cycle 2.
- Grade 5 toxicity

DLTs must be reported within 24 hours to the Sponsor as Events of Clinical Interest (see Section 7.2.3.2). If the event also meets the criteria for seriousness, follow the reporting guidelines for Serious Adverse Events (SAEs) outlined in Section 7.2.3.1.

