### 5.2.1.6 Dose Adaptation

The Common Terminology Criteria for Adverse Events version 4.0 (CTCAE 4.0) must be used to grade the severity of adverse events. MK-8628 will be withheld for drug related Grade 4 hematologic toxicities, non-hematological toxicity  $\geq$  Grade 3 including laboratory abnormalities, and severe or life-threatening AEs as per [Table 7](#) below. If a dose of MK-8628 is withheld for toxicity, then subjects may resume dosing with MK-8628 if that is appropriate at their next scheduled appointment or when toxicity has improved as described below.

Table 7: Dose Modification Guidelines for Drug-Related Adverse Events

Toxicity	Grade	Hold Treatment (Y/N)	Timing for restarting treatment	Dose/Schedule for restarting treatment	Criteria for discontinuation after consultation with Sponsor
Hematologic toxicity	1, 2	No	N/A	N/A	N/A
	3 associated neutropenia with infection; or thrombocytopenia with bleeding or lasting > 7 days	Yes	Toxicity resolves to Grade 0-1, or to baseline	Resume treatment at next lower dose level ( Table 8 )	Toxicity does not resolve within 2 weeks of last dose. Permanent discontinuation should be considered for any severe or life-threatening event
	4 or febrile neutropenia	Yes	Toxicity resolves to Grade 0-1, or to baseline	Resume treatment at next lower dose level ( Table 8 )	Toxicity does not resolve within 2 weeks of last dose. Permanent discontinuation should be considered for any severe or life-threatening event
Non-Hematologic	1, 2	No	N/A	N/A	N/A

Toxicity	Grade	Hold Treatment (Y/N)	Timing for restarting treatment	Dose/Schedule for restarting treatment	Criteria for discontinuation after consultation with Sponsor
Laboratory Abnormalities	3, 4  With or without symptoms lasting > 48 hours	Consider holding  Hold treatment for total bilirubin increases >2X ULN or 2X baseline (if elevated at baseline) and/or AST or ALT ≥ 5X ULN	Toxicity resolves to Grade 0-1, or to baseline	Laboratory abnormalities resolve within 1 week: treat at same dose and schedule  Laboratory abnormalities do not resolve within 1 week: may consider resuming treatment at next lower dose level (Table 8)	Toxicity does not resolve within 2 weeks of last dose. Permanent discontinuation should be considered for any severe or life-threatening event
Non-Hematologic toxicity	1 2	No	N/A	N/A	N/A

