### **5.6.1.2 Hepatic Laboratory Abnormalities**

All trial subjects with liver test abnormalities should be monitored weekly until all abnormalities return to normal or to the baseline state. For subjects with isolated total bilirubin increases >2X ULN or 2X baseline (if elevated at baseline), monitoring should be every 2 weeks until bilirubin returns to normal or to the baseline state. Drug induced liver injury (DILI) may develop or progress even after the causative drug has been stopped. Results should be recorded on the case report form and in the database. See Section 12.7 for guidelines on the handling of these events (potential Hy's law cases).

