#### **5.8 Subject Withdrawal/Discontinuation Criteria**

Subjects may withdraw consent at any time for any reason or be dropped from the trial at the discretion of the investigator should any untoward effect occur. In addition, a subject may be withdrawn by the investigator or the Sponsor if enrollment into the trial is inappropriate, the trial plan is violated, or for administrative and/or other safety reasons. Specific details regarding discontinuation or withdrawal procedures; including specific details regarding withdrawal from Future Biomedical Research, are provided in Section 7.1.4 – Other Procedures.

Subjects will continue study treatment until any of the following events at which point it will be definitively discontinued:

- Disease progression
- Unacceptable toxicity
- Subject withdrawal of consent
- Subject non-compliance
- Treatment interruption for > 2 weeks for toxicity (except in the event of perceived benefit, with Sponsor agreement)
- Recurrence of DLT despite dose reduction (except in the event of perceived benefit, with Sponsor agreement)

However, in case of investigator's perceived benefit for the subject, treatment continuation can be considered with dose reduction despite delay/interruption > 2 weeks or reoccurrence of a DLT with the same intensity after one dose reduction. The perceived benefit of the investigator is defined by 1) any objective tumor response, or 2) any tumor shrinkage not meeting standard response criteria, but which could improve with additional treatment, or 3)

any symptomatic improvement, which, in the investigator's opinion, could not be achieved by other means. If, in the cases described above, DLT recurs with the same intensity despite one dose reduction, a second dose reduction may be considered. The decision should be discussed with the Sponsor, but the final decision must be made by the investigator.

In all cases, the reason for and date of study treatment discontinuation must be recorded in the eCRF and source documented in the subject's medical records. As far as possible, there should be only one reason for treatment discontinuation. If there are several (e.g. concomitant progressive disease and toxicity), the primary one must be reported. The subject must be followed up to establish whether the reason was an AE, and if so, this must be reported as such.

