### **12.7.2 Introduction**

Hepatotoxicity is injury or damage to the liver that may be associated with impaired liver function [1]. Drug-induced hepatotoxicity is one of the most common causes of termination of drug development, a major reason for refusal of market authorization and for restricted use, and the single most important cause of the withdrawal of market authorization for products [2]. Thus, drug-induced hepatotoxicity is a major concern during the discovery, development to post-authorization phases of the product life cycle (excerpted from Draft Guidance Document, Hepatotoxicity of Health Products, Ministry of Public Health, Canada, December 2010)[3].

As stated in the United States Food and Drug Administration (FDA) “Guidance for Industry - Drug-Induced Liver Injury: Premarketing Clinical Evaluation” [4]; hepatocellular injury (usually detected by serum aminotransferase elevations [AT]) can be caused by drugs that rarely, if ever, cause severe DILI (e.g., aspirin, tacrine, statins, and heparin), as well as by drugs that do cause such injury. The frequency of serum AT elevations also is not a good indicator of a potential for severe DILI because drugs such as tacrine (not a cause of severe DILI) can cause AT elevations in as many as 50 percent of patients. Very high levels of observed ATs may be a somewhat better indicator of potential for severe DILI, but the most specific indicator is evidence of altered liver function accompanying or promptly following evidence of hepatocellular injury.

The single clearest (most specific) predictor found to date of a drug’s potential for severe hepatotoxicity, is the occurrence of hepatocellular injury (AT elevation) accompanied by increased serum total bilirubin (TBL) not explained by any other cause, such as viral hepatitis or exposure to other hepatotoxins, and without evidence of cholestasis, together with an increased incidence of AT elevations in the overall trial population compared to control. Increased plasma prothrombin time, or its international normalized ratio (INR), a consequence of reduced hepatic production of Vitamin K-dependent clotting factors, is another potentially useful measure of liver function that might suggest the potential for severe liver injury.

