### 12.7.5.3 Signs and Symptoms (associated with the potential DILI event)

Does the subject have a concomitant illness? Does the subject currently exhibit signs or symptoms of hepatitis/DILI? What are the subject's signs and symptoms (see examples below)? What are the pertinent findings from medical history, physical/laboratory examination (e.g., fatigue, nausea, vomiting, right upper quadrant pain or tenderness, fever, rash, and/or eosinophilia > 5%, hepatomegaly, splenomegaly, etc.) that could suggest DILI?

Category	Examples of Signs and Symptoms
Blood/lymphatic	Eosinophilia, coagulopathy, susceptibility to bleeding/bruising
Circulatory	Varicose veins, edema
Constitutional	Fever, fatigue, malaise, weight gain, other (identify).
Digestive/hepatic	Anorexia, diarrhea, bloody or black stool, light-colored stools, nausea, vomiting, hematemesis, upper quadrant abdominal pain, upper quadrant tenderness, hepatomegaly, jaundice, splenomegaly, ascites, cholestasis
Endocrine/reproductive	Loss of libido
Integumentary	Rash, pruritus
Muscular	Myalgia
Nervous	Changes in mental status or level of consciousness
Urinary	Dark urine

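### Two of the five liver DLT conditions trigger no mandatory in-cycle hold when they grade below 3 and bilirubin is under 2X ULN

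*Combined protocol and SAP*

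**What the plan says.** Section 5.2.1.4 lists five liver-test conditions that count as DLTs in Part A Cycle 1 if the investigator considers them related to MK-8628: ALT/AST >8X ULN; >5X ULN for more than 2 weeks; >3X ULN with bilirubin >2X ULN; >3X ULN with INR >1.5; and ALT/AST >3X "ULN with the appearance of fatigue, nausea, vomiting, right upper quadrant pain or tenderness, fever, rash and/or eosinophilia" above 5%. The last has an exception for rash or fatigue judged drug-related and not hepatic, with Sponsor agreement.

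Dosing after toxicity is governed by Section 5.2.1.6. Its lead-in withholds drug for non-hematologic toxicity of at least "Grade 3 including laboratory abnormalities, and severe or life-threatening AEs as per" Table 7. In Table 7 the hold entry for Grade 1-2 laboratory abnormalities is No. The Grade 3, 4 laboratory cell says to consider holding, then adds "Hold treatment for total bilirubin increases >2X ULN or 2X baseline (if elevated at baseline) and/or AST or ALT ≥ 5X ULN". Neither INR nor symptoms appear there.

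Section 12.7.3 advises stopping when ALT/AST ≥3X, bilirubin ≥2X and alkaline phosphatase <2X ULN occur together. Section 5.6.1.2 adds monitoring: "All trial subjects with liver test abnormalities should be monitored weekly until all abnormalities return to normal or to the baseline state". Section 5.8 lists unacceptable toxicity as a reason to discontinue, and subjects may also "be dropped from the trial at the discretion of the investigator should any untoward effect occur".

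**The concern.** The protocol classes both combinations as dose-limiting, drug-related liver events, yet the table that sites use for dosing can answer No for the same event. The DILI appendix treats the same findings as warning signs. Section 12.7.2 says that a raised prothrombin time or INR "is another potentially useful measure of liver function that might suggest the potential for severe liver injury". Section 12.7.5.3 asks about findings such as "fatigue, nausea, vomiting, right upper quadrant pain or tenderness, fever, rash, and/or eosinophilia > 5%, hepatomegaly, splenomegaly, etc.) that could suggest DILI".

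What is at stake is individual safety. A subject with a declared liver DLT could go on taking the full dose because no rule requires a pause. Liver effects are already known for this drug: Section 4.1.3 reports a Grade 3 hyperbilirubinemia/transaminitis DLT, and Section 4.2.2 names bilirubin increases and Factor VII decreases among the main dose-limiting toxicities in the hematologic study. Chemistry and INR are both scheduled on Days 8 and 15 of Cycle 1, so a laboratory event in this band would be seen but would have no prescribed dosing consequence.

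**Working it through.** The plan gives no figure on this point to reproduce. The check sets each liver DLT condition against each hold or stop rule.

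*Case examined:* ALT/AST >3X to <5X ULN for the last two conditions, bilirubin <2X ULN except where the condition itself requires more, and all components below Grade 3.

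| Liver DLT condition (5.2.1.4) | Table 7 numeric hold | 12.7.3 stop | Mandatory in-cycle hold |
|---|---|---|---|
| ALT/AST >8X | met (≥5X) | not needed | yes |
| ALT/AST >5X for >2 weeks | met (≥5X) | not needed | yes |
| >3X and bilirubin >2X | met (bilirubin) | met if ALP <2X | yes |
| >3X and INR >1.5 | not met | not met | no |
| >3X and symptoms or eosinophilia | not met | not met | no |

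The table applies Table 7's numeric thresholds at any grade, which is the reading kindest to the plan. Two of five conditions still remain uncovered.

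*Other routes to a hold.* Sections 2.1, 5.2.1.2 and 5.2.1.3 say that toxicity leads to dose or schedule modification, but they refer to 5.2.1.6 and 5.6.1.1, and 5.6.1.1 refers back to 5.2.1.6. Table 7 offers consideration of a hold for intolerable Grade 2 non-hematologic toxicity lasting more than 7 days. This is discretionary, and Grade 2 fatigue is handled as Grade 1. Section 5.2.2 delays the next cycle until recovery to baseline or Grade <2, so it acts at Day 22 and not within Cycle 1.

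*The grading assumption.* No CTCAE 4.0 cut-offs are printed. For ALT/AST there is indirect support, because the ≥5X hold sits in the Grade 3, 4 row. For INR there is none. If INR did reach Grade 3, the lead-in to 5.2.1.6 says to withhold while the laboratory cell says to consider holding, so the instruction would still be unclear.

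*Calendar bounds on exposure.* These count doses from the day of detection.
- Cycle 1: 21 days × 2 = 42 doses.
- Between weekly liver checks: 7 × 2 = 14; 14/42 = 33%.
- Detected Day 8, dosing Days 8-21: 14 × 2 = 28; 28/42 = 67%.
- Detected Day 15, dosing Days 15-21: 7 × 2 = 14; 14/42 = 33%.
- Extremes of the ±3-day windows: Day 5, 17 × 2 = 34 (81%); Day 18, 4 × 2 = 8 (19%).

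The figures from Day 8, Day 15 and the window extremes require the subject to stay in the band with nobody using discretion.

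*Effect of a hold on the primary endpoint.* The missed-dose DLT criterion is 20% × 42 = 8.4, so 9 or more doses; a 5-day hold misses 10. A Part A Cycle 1 subject held for one of these conditions is already a DLT, so the net change in the DLT count is 0. Section 8.5.2 keeps anyone with a DLT in the evaluable population.

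**The case against.** The strongest reply is that a DLT definition governs escalation while a hold table governs individual dosing, and a more sensitive DLT definition is a legitimate choice. Entry permits ALT/AST up to just under 3X ULN and gastrointestinal toxicity is a known effect, so a small rise with mild nausea could meet the symptom condition. The DILI passages are regulatory background and history-taking prompts, not hold rules, and the appendix's own stop threshold requires bilirubin. Sites are also not left without support: DLTs are reported within 24 hours, and adverse events and blood counts are reviewed on Days 1, 4, 8, 11, 15 and 18, so symptoms and eosinophils are seen more often than chemistry.

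Much of this stands. It argues against a mandatory hold in every cycle and in Part B. It does not explain why an event already declared a drug-related liver DLT should meet a No in the dosing table.

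A reader might infer that the protocol obliges such a subject to continue at full dose. It does not: Table 7 is titled as guidelines, unacceptable toxicity in Section 5.8 requires discontinuation, and investigator discretion remains. A reader might also infer a required dose reduction after a first DLT from "Recurrence of DLT despite dose reduction (except in the event of perceived benefit, with Sponsor agreement" in Section 5.8. That clause addresses recurrence after a reduction and does not prescribe one.

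**Conclusion.** The point holds as an inconsistency between the DLT definition and the dosing rules: two of five liver DLT conditions have no mandatory in-cycle hold in the band ALT/AST >3X to <5X ULN with bilirubin <2X ULN. It rests on the components grading below 3, with the INR condition less certain, and on Figure 5 adding no hold. Confidence is medium.

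Its practical size is modest. Weekly monitoring would show progression to a hold threshold, no case in this band is documented, and the number of subjects affected cannot be derived from the documents. The hepatic DLT reported in Section 4.1.3 was Grade 3, which the existing rules already address.

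A reader might infer that escalation or the RP2D is compromised. The documents do not support that, because these events are counted as DLTs whether or not drug is held. Nor does the argument carry over in full to Part B or later cycles, since 5.2.1.4 defines DLTs only for Part A Cycle 1. The correction is a cheap safety improvement that should be made; it does not repair the primary analysis.

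**What to change.** First check Figure 5. If it already shows a hold for these conditions, align Table 7 with it. Otherwise:

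- In the hold cell of the Table 7 laboratory row, add: *also hold, regardless of grade, for any Part A Cycle 1 event that meets a liver DLT criterion in 5.2.1.4 (same rash/fatigue exception)*. Mark the Grade 1-2 No entry *except as stated below*.
- Leave restart to the existing laboratory-row rules: recovery to Grade 0-1 or baseline, same dose if resolved within 1 week, otherwise the next lower level may be considered. No dose reduction becomes mandatory.
- For Part B and later cycles, use *consider holding* on the same criteria, with INR where it is measured. PT/INR is scheduled only at screening and in Cycles 1-2, and an obligatory pause for a mild event is harder to justify in NMC, where Section 4.1.1.1 gives a median survival of 6.7 months.

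The cost is one phrase and one cross-reference for the Cycle 1 rule plus a line for the other settings, with no new tests, visits or subjects. Some Cycle 1 dosing will be interrupted: up to 14 doses if the event resolves within a week, more otherwise. An interruption beyond 2 weeks would meet the existing discontinuation rule unless the Sponsor agrees to continue.

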### 5.2.1.5 Recommended Phase II Dose

The recommended phase II dose (RP2D) will be determined based on a multi-faceted decision taking into account safety, tolerability, early efficacy signal, PK exposure and PD markers. The primary endpoint driving dose selection is the DLT rate, with weight given to the highest DL tolerated (<25% DLT rate). All other facets will be considered supportive. It is important to note that dose selection in this study aims to assess a RP2D *range*, with other factors aside from those mentioned above, such as target engagement, contributing to refining the dose selection for phase 2. This will be further evaluated in subsequent clinical investigations in either monotherapy or combination trials.

### 5.2.1.6 Dose Adaptation

The Common Terminology Criteria for Adverse Events version 4.0 (CTCAE 4.0) must be used to grade the severity of adverse events. MK-8628 will be withheld for drug related Grade 4 hematologic toxicities, non-hematological toxicity  $\geq$  Grade 3 including laboratory abnormalities, and severe or life-threatening AEs as per [Table 7](#) below. If a dose of MK-8628 is withheld for toxicity, then subjects may resume dosing with MK-8628 if that is appropriate at their next scheduled appointment or when toxicity has improved as described below.

Table 7: Dose Modification Guidelines for Drug-Related Adverse Events

Toxicity	Grade	Hold Treatment (Y/N)	Timing for restarting treatment	Dose/Schedule for restarting treatment	Criteria for discontinuation after consultation with Sponsor
Hematologic toxicity	1, 2	No	N/A	N/A	N/A
	3 associated neutropenia with infection; or thrombocytopenia with bleeding or lasting > 7 days	Yes	Toxicity resolves to Grade 0-1, or to baseline	Resume treatment at next lower dose level ( Table 8 )	Toxicity does not resolve within 2 weeks of last dose. Permanent discontinuation should be considered for any severe or life-threatening event
	4 or febrile neutropenia	Yes	Toxicity resolves to Grade 0-1, or to baseline	Resume treatment at next lower dose level ( Table 8 )	Toxicity does not resolve within 2 weeks of last dose. Permanent discontinuation should be considered for any severe or life-threatening event
Non-Hematologic	1, 2	No	N/A	N/A	N/A

Toxicity	Grade	Hold Treatment (Y/N)	Timing for restarting treatment	Dose/Schedule for restarting treatment	Criteria for discontinuation after consultation with Sponsor
Laboratory Abnormalities	3, 4  With or without symptoms lasting > 48 hours	Consider holding  Hold treatment for total bilirubin increases >2X ULN or 2X baseline (if elevated at baseline) and/or AST or ALT ≥ 5X ULN	Toxicity resolves to Grade 0-1, or to baseline	Laboratory abnormalities resolve within 1 week: treat at same dose and schedule  Laboratory abnormalities do not resolve within 1 week: may consider resuming treatment at next lower dose level (Table 8)	Toxicity does not resolve within 2 weeks of last dose. Permanent discontinuation should be considered for any severe or life-threatening event
Non-Hematologic toxicity	1 2	No	N/A	N/A	N/A
Note: Exception to be treated similar to Grade 1 toxicity 
 
• Grade 2 alopecia
 
• Grade 2 fatigue
 
	Any intolerable G2 non-hematologic toxicity lasting >7 days with or without dose reduction	Consider holding for persistent symptoms	Toxicity resolves to Grade 0-1 or baseline	Clinical AE resolves within 2 weeks: treat at same dose and schedule  Clinical AE does not resolve within 2 weeks: may consider resuming treatment at next lower dose level (Table 8)	Dose is interrupted for > 2 weeks.
	3, 4  Unless not optimally treated with supportive care (e.g. Grade 3 vomiting not adequately treated according to anti-emetic standard of care)	Yes	Toxicity resolves to Grade 0-1 or baseline	Resume treatment at next lower dose level (Table 8)	Toxicity does not resolve within 2 weeks of last dose. Permanent discontinuation should be considered for any severe or life-threatening event

After recovery from toxicity, treatment will be resumed at the next lower dose level (Table 8). For subjects treated at DL1 (20 mg BID), 10 mg BID will be evaluated.

Table 8: MK-8628 Dose and Schedule Modifications

Dose Level (DL)	Initial Dose	1st Modification
DL 1	20 mg BID continuous	10 mg BID continuous
DL 2	30 mg BID continuous	20 mg BID continuous
DL 3	40 mg BID continuous	30 mg BID continuous

Note: Dose modification for 10 mg BID continuous will only include dose interruption and no further reduction is allowed.

For subjects enrolled in Part B of the study (NMC Cohort), the same guidelines for dose modifications should be followed.

No more than one dose reduction should be implemented unless the investigator thinks it in the subject's best interests to pursue study treatment with further dose reduction (additional dose reduction by one dose level), with the Sponsor's agreement.

Dosing interruption for > 2 weeks due to toxicity will lead to definitive study treatment discontinuation, unless the investigator thinks it in the subject's best interests to pursue study treatment, with the Sponsor's agreement.

